Nature and extent of the burden and risks associated with participation, benefit and group relatedness: Eight blood samples of 6 ml full venous blood obtained by vena

puncture per intervention per individual, 2 times in a cross-over pilot study, in which interventions are 3 weeks apart (so 2 x 8 samples in 10 volunteers). Risk of vena puncture is negligible, idemque the burden.

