2. OBJECTIVES

Primary Objective:

To determine whether a plasma lycopene concentration can serve as a response parameter after a single dose of dietary lycopene.

Secondary Objectives:

1. To determine if a food supplement tablet lycopene with equivalent lycopene content compared to a single dose dietary intervention provides identical plasma lycopene concentration responses compared to the dietary intervention.
2. To determine the influence of prior food consumption, as measured by dietary questionnaires, on plasma lycopene levels before and after lycopene intervention.

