3. STUDY DESIGN

Cross-over interventional pilot study.

Ten healthy individuals (male 18-75 years) are randomly divided in two groups (A and B) of 5 individuals. One week before the dietary intervention a daily food questionnaire will be completed.

One hour before the intervention a blood sample will be taken (all blood samples 6 ml EDTA plasma tube). All individuals will be given an infusion needle for 26 hours. Samples are spun and plasma is pipetted and distributed over 1 ml Eppendorf cups for immediate freezing at -80 Celsius at the research lab.

Group A will take 40 mg lycopene (2,5 pills of food supplement Vitabiotics Ultra Lycopene 15mg, potent extract). Group B will take 250 ml of tomato soup (matching with 40 mg lycopene) with 20 ml olive oil. Blood sampling as described in all individuals from needle: 1,3,6,12,24 hours after intervention, and after 48 and 72 hours by direct venapunction. Wash out period of 3 weeks, after which the identical above procedure takes place including questionnaires, but group A and B changed (cross-over). All samples (n=160) will be frozen at -80, and transported on dry ice to Wageningen University for lycopene determination.

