8.3 Study procedures

Participants will be randomized into the study scheme AB versus BA (cross-over). One week before the intervention a food frequency questionnaire will be distributed to participants. Group A will take 40mg lycopene (2,5 pills of food supplement Vitabiotics Ultra Lycopene 15mg, potent extract). Group B will take 250 ml of tomato soup (matching with 40mg lycopene) with 20ml olive oil. Wash out period of 3 weeks, after which the identical procedure takes place including questionnaires, but group A and B changed (cross-over).

Blood draws are taken on indicated time points (before intervention, 1, 3, 6, 12, 24, 48 and 72 hours after intervention) in standard vacutainers (BD Vacutainer; Becton, Dickinson and Company). For the first blood draws (before intervention and 1-24 hours

after the intervention) all participants will be given an infusion needle for 26 hours. Blood draws after 48 and 72 hours will be done by direct venapunction. Next, the tubes are centrifuged at 3000g for 10 minutes at 4 °C (Sigma 4-16K; Sigma-zentrifugen). Plasma samples are immediately put on dry ice for rapid freezing. At the end of each test day, the plasma samples are stored at -80 °C until further analysis.

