Standard liquid-chromatography-based technology for the analysis of carotenoids and similar structures including lycopene. Plasma carotenoids, including retinol, alpha- and beta-carotene, beta-cryptoxanthin, lutein, lycopene, tocopherols and zeaxanthin, are determined using ultra-pressure liquid chromatography coupled to diode array detection (UPLC-DAD). In short, 375 µL plasma is denatured using ethanol in the presence of the internal standard retinyl acetate. The carotenoids are subsequently extracted using 0.01% w/v butylated hydroxytoluene in hexane. The extracts are dried under nitrogen in a TurboVap evaporator (Biotage, Uppsala, Sweden) at 35 °C, reconstituted in acetonitrile, and transferred to a LC vial. LC analysis is performed on a Acquity H-class UPLC coupled to an Acquity PDA eLambda detector (Waters, Etten-Leur, the Netherlands) using an Acquity UPLC HSS T3 column (Waters). Gradient elution is performed using a mixture of acetonitrile-dichloromethane-methanol (ratio 85:5:10) containing 0.1% ammonium acetate (eluens A) and ULC-MS grade water (eluens B) with a constant flow of 400 µL/min and a runtime of 30 min. The detector is set at 292, 325 and 450 nm. Concentrations are calculated using a 6-point calibration curve. A pooled plasma sample is analyzed in duplicate in each analytical batch to monitor the quality of the analyses.

An extensive Food Frequency Questionnaire (FFQ) will be used to assess the participants' habitual diet of the previous month. This extensive FFQ was validated for energy, macronutrients, and a number of vitamins [14-17] and administered online with the self-administered Dutch FFQ-tool™ [18], one week prior to the intervention. Participants indicate the frequency of consumed food items by selecting answers ranging from 'not consumed' to '7 days per week' and portion sizes can be estimated using natural portions and commonly used household measures. The Dutch Food Composition Database (i.e., NEVO) will be used to calculate energy and nutrient content of foods.

During the intervention, participants will report their food intake in a smartphone-based food diary on the first day of the intervention and the two following days. For this purpose, Traqq® will be used, an ecological momentary dietary assessment app [19]. In the morning, participants will receive a notification on their smartphone from Traqq®, inviting them to report their food intake during that day. Participants report their food intake by

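### The one-month food questionnaire repeated before period 2 looks back over the period-1 study dose, so the second habitual lycopene estimate can include the study soup

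*Protocol*

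**What the plan says.** Section 8.3 is the only place in the protocol that describes the questionnaire. It gives the reference period ("An extensive Food Frequency Questionnaire (FFQ) will be used to assess the participants' habitual diet of the previous month"), the timing ("one week prior to the intervention") and the nutrient source ("The Dutch Food Composition Database (i.e., NEVO) will be used to calculate energy and nutrient content of foods"). The same section says earlier: "One week before the intervention a food frequency questionnaire will be distributed to participants".

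The questionnaire is repeated in period 2. Section 3 reads "Wash out period of 3 weeks, after which the identical above procedure takes place including questionnaires, but group A and B changed (cross-over"), and section 8.3 says the same. On spacing, the Summary describes the blood sampling as done "2 times in a cross-over pilot study, in which interventions are 3 weeks apart".

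The questionnaires serve secondary objective 2 in section 2: "To determine the influence of prior food consumption, as measured by dietary questionnaires, on plasma lycopene levels before and after lycopene intervention". Section 8.1.2 lists the matching secondary endpoint. Section 10.2 says that questionnaire and diary data will be described only.

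Two other places label the instrument differently. Section 3 has "One week before the dietary intervention a daily food questionnaire will be completed", and section 8.1.3 speaks of weekly questionnaires. Neither describes an instrument or a look-back period.

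**The concern.** Habitual diet means what a man usually eats. A single dose supplied by the investigators is not part of it. If the month covered by FFQ 2 contains the day of the first dose, a man who ate the study soup may report it as tomato soup eaten in that month. His period-2 habitual lycopene figure then carries part of the intervention.

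Secondary objective 2 sets this figure against plasma lycopene before and after the dose. Research question 3 in section 1 also suggests that a man with an existing high questionnaire intake might be left out of further supplementation. Because soup is a food and a tablet may not fit a food list, any error would arise mainly in the soup-first men and so could follow treatment sequence.

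The timing and reference period of the instrument are fixed in the protocol itself, so this is not a detail that would normally wait for a statistical analysis plan.

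**Working it through.** The protocol gives no figure to reproduce here. The check is calendar arithmetic followed by a simple load calculation.

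**Inputs.** Look-back M of one month, taken as 28 to 31 days (section 8.3). Questionnaire 7 days before each dose (section 8.3). Doses G days apart, with G = 21 from the Summary. The washout wording in sections 3 and 8.3 would also allow the three weeks to run from the 72-hour sample, or the questionnaire week to follow the washout, so larger values of G are tried too.

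**Overlap.** Let day 0 be dose 1. FFQ 2 falls on day G − 7 and its window opens on day G − 7 − M.

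| Reading | G | FFQ 2 on day | Window opens (M = 31 to 28) | Day 0 inside? |
|---|---|---|---|---|
| Doses 21 days apart | 21 | 14 | −17 to −14 | yes |
| 21 days from the 72-hour sample | 24 | 17 | −14 to −11 | yes |
| Questionnaire after the 3-week washout, dose a week later | 28 | 21 | −10 to −7 | yes |
| Both of the last two | 31 | 24 | −7 to −4 | yes |

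Dose 1 drops out of the window only if G − 7 − M > 0, that is G > M + 7 = 35 to 38 days. The first questionnaire is on day −7, before any study product, so it is clean.

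**Sensitivity to the label.** With a one-week look-back, FFQ 2 on day 14 would cover days 7 to 14 and dose 1 would lie outside. The point therefore rests on the one-month definition in section 8.3.

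**Size if one portion is reported and counted once.**
- Coded as ordinary tomato: section 6.1 gives 8.4 mg per 100 g for the study tomato, three times the supermarket level, so 8.4/3 = 2.8 mg per 100 g. Taking 250 ml as 250 g (assumption), 2.5 × 2.8 = 7 mg. Spread over the month: 7/31 = 0.23 to 7/28 = 0.25 mg/day.
- Credited in full: 40/31 = 1.29 to 40/28 = 1.43 mg/day.
- A tablet dose, if it were entered at all: 2.5 × 15 = 37.5 mg, giving 37.5/31 = 1.21 to 37.5/28 = 1.34 mg/day.

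The documents do not settle which coding applies. Section 8.3 names the food composition database but gives no lycopene value from it. Section 1 puts 200 g of tomato soup at about 33 mg, which scales to 33 × 250/200 = 41 mg, close to the full dose.

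**Relative size, illustration only.** The protocol gives no habitual intake. Over 30 days the load is 7/30 = 0.23 or 40/30 = 1.33 mg/day. At an assumed 10, 5 or 2 mg/day this is 2%, 5% or 12% at the low end, and 13%, 27% or 67% at the high end.

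**The case against.** The strongest reply is that overlap is not yet error. The questionnaire asks about habitual diet, and a man may well see that one supervised portion does not belong there. Harm requires that he reports it, that the tool can record one portion in a month, and that the analyst leaves it in. None of these is shown. A completion instruction may also sit in the information leaflet or the online tool, neither of which is at hand. This stands as a limit on the consequence. It does not remove the overlap, and if some men count the soup and others do not, the described procedure does not record who did.

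A second reply is that secondary objective 2 concerns prior food consumption, and the first study dose is real prior lycopene intake in period 2. That is fair, and it argues against simply discarding the dose. But the dose is known for every man, so it can be recorded exactly and kept apart from habitual diet.

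A reader might go further and infer that period-2 intake is overstated by up to two thirds, or that a bias between sequences is established. The documents support neither. The 67% figure combines full crediting with the lowest assumed intake, and how five men would report soup as against tablets is conjecture. Nor does it follow that the first questionnaire must be the only measure: it would be 21 + 7 = 28 days old at the second baseline sample, so that choice is a trade-off.

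**Conclusion.** The overlap is certain given the one-month look-back in section 8.3: FFQ 2 falls 14 to 24 days after dose 1, and its window contains that dose on every reading of the washout. No text in the protocol excludes the study product. The period-2 habitual lycopene intake can therefore include the study soup, mainly in the soup-first men.

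The consequence is conditional. It assumes that one portion is reported and counted once, and it then amounts to about 0.2 to 1.4 mg/day depending on coding. Percentages cannot be fixed from the documents.

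The point is minor. Questionnaire data are only described, the first questionnaire is unaffected, dose dates and sequence are known, and the primary endpoint does not use these data. It is still worth correcting, because a reported portion cannot be reliably separated out afterwards.

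**What to change.** Add to section 8.3: *In the second food frequency questionnaire, do not count the study soup or the study tablets. The period-1 study dose is recorded separately, with its date, as known prior lycopene intake.*

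Both questionnaires and the three-week interval stay. Lengthening the interval beyond 35 to 38 days would also remove the overlap, but it is out of proportion to the problem. Bringing the daily and weekly labels in sections 3 and 8.1.3 into line with section 8.3 is a separate clerical matter.

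The cost is a short text edit, with no extra visit, sample or participant. The downside is that it relies on the men following the instruction.

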8.4 Withdrawal of individual subjects

Subjects can leave the study at any time for any reason if they wish to do so without any consequences. The investigator can decide to withdraw a subject from the study for urgent medical reasons.

8.4.1 Specific criteria for withdrawal

Not applicable.

8.5 Replacement of individual subjects after withdrawal

Only withdrawal of subjects before the first plasma determination (T0) will lead to replacement. After evaluation of results of 10 minus 3 subjects new participants will be reconsidered.

8.6 Follow-up of subjects withdrawn from treatment

Incomplete data will be used only with their consent, otherwise destroyed.

8.7 Premature termination of the study

There are no conditions defined for premature stopping the study. Data will be kept for 15 years as described on the patient information leaflet. Blood samples will be kept for 2 years to perform new analyses if needed. If, due to premature termination of the study, this will no longer be needed, the samples will be destroyed.

9. SAFETY REPORTING

9.1 Temporary halt for reasons of subject safety

In accordance to section 10, subsection 4, of the WMO, the sponsor will suspend the study if there is sufficient ground that continuation of the study will jeopardise subject health or safety. The sponsor will notify the accredited METC without undue delay of a temporary halt including the reason for such an action. The study will be suspended pending a further positive decision by the accredited METC. The investigator will take care that all subjects are kept informed.

9.2 AEs, SAEs and SUSARs

9.2.1 Adverse events (AEs)

Adverse events are defined as any undesirable experience occurring to a subject during the study, whether or not considered related to the investigational product / trial procedure/ the experimental intervention. All adverse events reported spontaneously within a period of 1 week after consuming the soup or taking the food supplement (including blood drawing afterwards) by the subject or observed by the investigator or her staff will be recorded.

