6.3 Summary of findings from clinical studies

Food supplement Vitabiotics Ultra Lycopene, 15mg, potent extract: we are not aware of any performed clinical studies.

Harvest of Health tomato: to the knowledge of the research group, no clinical studies have been done with the Harvest of Health (Proudesse) tomato.

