13. STRUCTURED RISK ANALYSIS

13.1 Potential issues of concern

There are no potential issues of concern.

a. Level of knowledge about mechanism of action

There is no adverse effect of lycopene known at a dose of 40 mg/day.

b. Previous exposure of human beings with the test product(s) and/or products with a similar biological mechanism

No adverse effects observed.

c. Can the primary or secondary mechanism be induced in animals and/or in ex-vivo human cell material?

Not in relation to life style compliance.

d. Selectivity of the mechanism to target tissue in animals and/or human beings

-

e. Analysis of potential effect

-

f. Pharmacokinetic considerations

Previously used pharmacokinetic schedule for plasma biomarkers being used.

g. Study population

Healthy subjects.

h. Interaction with other products

Unknown.

i. Predictability of effect

The changes in plasma carotenoid concentrations are unpredictable, and are potentially influenced by prior food consumption.

j. Can effects be managed?

-

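### Adverse events are recorded only if volunteered or observed, so mild complaints may be missed; one neutral question at the existing post-dose draws would make the record firmer

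*Protocol*

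**What the plan says.** Protocol section 9.2.1 defines an adverse event broadly, as "any undesirable experience occurring to a subject during the study", and then states how events enter the record. There are two routes. The first is the man himself: "All adverse events reported spontaneously within a period of 1 week after consuming the soup or taking the food supplement". The second is staff; the sentence ends "by the subject or observed by the investigator or her staff will be recorded". It expressly includes the blood drawing that follows each intake.

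Section 8.3 sets the contacts: draws are taken "before intervention, 1, 3, 6, 12, 24, 48 and 72 hours after intervention". The draws up to 24 hours use an indwelling needle; for the last two, "Blood draws after 48 and 72 hours will be done by direct venapunction". The same schedule is repeated with the other product after a three-week wash-out.

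On prior experience, section 6.3 says the research group is unaware of any clinical study of the supplement and that, to its knowledge, "no clinical studies have been done with the Harvest of Health (Proudesse) tomato". Section 13.1, item b, says "No adverse effects observed" under a heading that covers the test products and also products with a similar mechanism. Section 1 describes earlier human exposure to lycopene itself, at high doses over several weeks, without toxicity.

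Sections 2 and 8.1 list no safety or tolerability objective or endpoint. Section 10 plans no statistical calculations.

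**The concern.** The broad definition and the narrow route into the record do not fit well together. An undesirable experience that only the man can feel, such as mild nausea, bloating or discomfort, counts as an event under the definition. It is recorded only if he raises it unprompted. No section describes a symptom question, a checklist or an adverse-event diary, and the smartphone diary in section 8.3 is for food intake.

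This is avoidable, because a staff member is with each man repeatedly after each dose. At stake is how far the adverse-event listing can be read. An empty or short listing would not distinguish men who had no complaint from men who were not asked. Soup and tablets are plainly different to the men taking them, so readiness to speak up could also differ by product. Any descriptive remark on how the two were tolerated would carry that uncertainty.

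**Working it through.** **1. What the passive method can and cannot record.** Setting the routes in section 9.2.1 against the types of event:

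| Type of event | Volunteered by the man | Observed by staff |
|---|---|---|
| Visible, e.g. at the needle site | possible | likely during draws |
| Subjective and mentioned | yes | not needed |
| Subjective and not mentioned | no | no |

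The last row is the gap. The method can lose such events, so as a measure of them the count is a lower bound.

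**2. Contacts already scheduled.** The Summary gives ten men and eight draws in each of two periods ("so 2 x 8 samples in 10 volunteers"). 10 x 2 x 8 = 160, which agrees with the 160 samples in section 3. Seven of the eight draws follow intake: 10 x 2 x 7 = 140 post-dose contacts, or 70 per product.

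**3. How much of the window those contacts cover.** The recording window is one week, 7 days. The last draw is at 72 hours, day 3. That leaves 7 - 3 = 4 days of each window with no scheduled contact. In period 1 the next contact is the pre-dose draw of period 2. With intakes three weeks apart (Summary), that is about 21 - 7 = 14 days after the first window closes. Period 2 has no later contact.

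**4. Illustration of size.** The protocol gives neither an event rate nor a capture share, so there is no figure of its own to reproduce, and both inputs are assumptions. Let p be the true share of men with an event on one product, and c the chance that an affected man is recorded, independently between men. Each man is then recorded with probability p x c.

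- Zero recorded in ten, complete capture: the one-sided 95% upper bound solves (1 - U)^10 = 0.05, so U = 1 - 0.05^(1/10) = 0.259.
- With capture c, the bound on the true rate is U / c.
- Chance of recording nothing at all: (1 - p x c)^10. For example, p = 0.20 and c = 0.5 give 0.90^10 = 0.349.

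| Assumed c | Upper bound on p if 0/10 recorded | P(nothing recorded), p = 10% | p = 20% | p = 30% |
|---|---|---|---|---|
| 1.0 | 25.9% | 34.9% | 10.7% | 2.8% |
| 0.8 | 32.4% | 43.4% | 17.5% | 6.4% |
| 0.5 | 51.8% | 59.9% | 34.9% | 19.7% |
| 0.3 | 86.3% | 73.7% | 53.9% | 38.9% |

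The first row matters as much as the others: even with perfect capture, ten men leave rates up to about 26% open.

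**The case against.** The strongest reply is that this is a defensible choice and not an error. Section 9.2.1 is clear, the monitoring section (12.2) classes the study as negligible risk, the interventions are single servings in healthy men, and no planned conclusion uses adverse-event counts. Staff who handle an indwelling needle for a day and then perform two venepunctures will probably see needle-site problems. A symptom question could be put on the case report form without changing the protocol. The sample is so small that no method of asking would support a reassuring safety claim.

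Most of this stands, and it limits the point to a cheap improvement. It does not remove the gap for subjective complaints, because the protocol positively states a method that does not ask.

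A reader might also infer more than the text supports:

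- *That events will be undercounted.* The text shows only that they may be. All the men might report everything.
- *That this is the first safety record of these products.* Section 6.3 reports what the group is aware of. The supplement is bought in a store (section 6.8), and lycopene itself has prior human exposure (sections 1 and 13.1).
- *That sections 6.3 and 13.1 contradict each other.* They do not, because the heading of 13.1 item b extends to similar products.
- *That a clean record would be carried into the prostate cancer study as safety evidence.* Section 1 names technology, logistics, food products and the lycopene marker as what is taken forward, and section 12.6 speaks only of using the data to continue that study. Neither mentions safety evidence.
- *That the percentages describe this trial.* They follow from assumed capture shares.

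**Conclusion.** The point holds as a minor one. Collection under section 9.2.1 is passive, the men are seen seven times after each dose without a stated question, and mild subjective events may therefore be missed. For the two specific products, of which the research group knows no clinical studies, a better record is worth having at this price.

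The direction of any error is known (downward) but its size is not. Under the assumptions above, an empty listing for one product would exclude rates above 26% with complete capture and only above 52% with half. The primary and secondary lycopene results do not depend on this. Only the adverse-event listing and any tolerability statement drawn from it do.

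**What to change.** In section 9.2.1, keep the spontaneous and observed routes and add:

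- One neutral open question, such as how the man has felt since the last draw, at every post-dose draw in both periods, asked in the same words for both products. Record the answer each time, including none.
- At the existing pre-dose draw of period 2, a question on the rest of the first one-week window. The recall gap is about two weeks, so the answer should be marked as recalled.
- A statement that after 72 hours in period 2 capture is spontaneous only. Alternatively, one brief message at day 7, preferably in both periods so that the products are treated alike.
- Descriptive reporting of events per product, with the number of men asked, and with prompted and spontaneous reports kept apart.

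The cost is one form line at 140 contacts that already take place, plus up to 2 x 10 = 20 short messages if the day-7 option is used in both periods. No extra visit or blood is needed. The downside is that more minor, unrelated events will be recorded and must be followed up under section 9.4.
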